4. **Evaluation of the Implementation Process – Qualitative Interviews.** At 6-8 months following the start of the implementation process of each app at the 3 early adopter sites, we will conduct follow-up semi-structured qualitative telephone individual interviews among the core implementation team, 3 PCPs, 3 dermatologists, 2 dermatology staff members, as well as leadership positions overseeing and supporting teledermatology operations at each site to assess OTIE factors suggestive of implementation success. The goal will be to interview the same individuals interviewed at baseline. The follow-up guide to be used for these interviews has not yet been developed as it will necessarily need to reflect the information obtained in the initial baseline studies above, but will in general allow participants to expand on the same areas covered by the bi-monthly site report survey that is attached, and described in (3) above. The follow-up interview will be introduced by the telephone consent script attached to this application.
5. **Assessment of Sustainability.** At one year, we will assess the sustainability of use of each of the mobile apps.
 1. The Mancini & Marek Model of Community-based Program Sustainability will be used to conceptually guide the evaluation of sustainability. Mancini & Marek propose that six elements are important to achieve long-term sustainability: Leadership competence, effective collaboration, demonstrating program results, strategic funding, staff involvement and integration, and program responsiveness. The validated Program Sustainability Index (PSI) measures each of the 6 sustainability elements, and is attached to this application. Each core implementation team member and director of primary care and dermatology will be surveyed for each app.
 2. Using the semi-structured interview methods above, each core implementation team member, director of primary care, Chief of Dermatology, FTC, imager, and other staff members participating in processing or supporting teledermatology at each site will be interviewed. The sustainability interview will explore in more depth the areas surveyed in the PSI (Leadership, Collaboration, Demonstrating Program Results, Funding, and Program Responsivity). We have previously used the combination of PSI and qualitative interviews to evaluate the sustainability of a multi-facility program for the Office of Patient Centered Care and Cultural Transformation. This program sustainability interview guide will be introduced by the telephone consent script attached to this application.

Sub-Aim 2.2

Implementation of field sites will also be assessed at all participating sites by monitoring intermediate milestones and quantitative indicators of implementation that are available in CDW as well as from OCC's own telehealth database and Web and Mobile Solutions (WMS) device procurement program.

To understand how rapidly sites meet key milestones as a result of the OCC implementation process, and if the apps are more effective among sites that have reached more implementation milestones, randomized sites will be asked to complete a bi-monthly implementation site report monitoring key milestones, collected electronically via REDCAP on the VA intranet. This bi-monthly report is based on the bi-monthly site report utilized as part of the formative evaluation described above. Sites will be sent email reminders two weeks and one week prior to, and one week after the due date, with follow up via phone call, if necessary. Four of these randomized sites will be recruited to participate in semi-structured sustainability interviews using the same guides used in the formative evaluation and will be introduced by the telephone consent script attached to this application. These Interview data will be collected by

recording phone conversations directly onto secure VA networked servers or encrypted computers, using MS Teams and Phillips recorder.

8.11 INSTRUMENTS: List all questionnaires, surveys, interview, or focus group guides that will be used for this study:

If the instruments are not complete or not available because they will be developed as part of this study, describe the basic content or include an outline and submit the final versions to the IRB with a modification for approval prior to use.

- 1) Site Information Report (revision attached)
- 2) Site Process Guide (attached)
- 3) Organizational Readiness for Change (ORC) Survey (revision attached)
- 4) Initial Interview Guide (attached)
- 5) Bi-Monthly Site Report (survey revision attached)
- 6) Follow-up Interview Guide (Allows participants to expand on the same areas covered by the bi-monthly site report)
- 7) Program Sustainability Index (survey revisions attached) Now VA T Program Sustainability index (attached) and My T Program Sustainability index (attached)
- 8) Sustainability Interview Guide (attached-Allows participants to expand on the same areas covered by the PSI survey)
- 9) Bi-Monthly Site Report for National Sites (attached)

Telephone/Email Consent Scripts for Contacting Subjects:

- 1) Email consent script (introduction and consent to ORC, both Bi-monthly reports, and Program Sustainability Index surveys)
- 2) Telephone consent script (introduction and consent to Site Process Guide, Initial Guide, Follow-up Guide, and Sustainability Guide)

Attach any unpublished instruments in the 'Other Study Documents' section of the Initial Review Submission Packet form after completing the study application. Published instruments should NOT be attached.

8.12 * BIOSPECIMEN COLLECTION: Are you drawing any blood or collecting other biosamples (e.g. tissue, buccal swabs, urine, saliva, hair, etc.) for analysis under this protocol and/or storage for future research: (REQUIRED)

Yes No

8.13 STATISTICAL METHODS: Briefly summarize the methods and types of analyses that will be performed:

Aim 1-Due to a lack of participation by sites during the study which was in part conducted during the novel coronavirus (COVID-19) pandemic, we were not able to follow the analysis plan for Aim 1 described below. Instead we focused on understanding factors associated with successful completion of consults with the mobile apps, examining differences between rural and urban Veteran users.

Data analysis. Primary data will be collected and analyzed by CAPER and shared in aggregate with the PIs and other investigators. Stepped wedge - cluster randomized trials (SW-CRTs) need to employ data analysis strategies that account for the causal structure implied by this design and mitigate its potential shortcomings. Two related issues which may confound the treatment effect are the within-cluster correlation and potentially significant secular trends in the outcomes of interest given the long duration of the trials (2.5 years). In fact, the exposure of each cluster to both the control and intervention allows the researcher to partially exploit the within cluster variance towards estimation, which renders this type of trial less sensitive to the intra-cluster correlation coefficient. To further ensure that these confounding factors are properly handled, we will analyze the data using mixed models that allow for time fixed effects and cluster random effects.

Second, we are interested in the average effect of the treatment among compliers (patients who only receive the treatment as a direct result of their exposure to the intervention), referred to as the Local Average Treatment Effect (LATE). This effect better reflects the efficacy of teledermatology compared to regular practice. In order to estimate LATE, we will follow an instrumental variable (IV)-based two-stage residual inclusion (2SRI) procedure.

Finally, we will also conduct an intent-to-treat analysis, yielding an estimate of the average effect of being randomized to receive one of the telederm apps (average treatment effect). From a policy perspective, this effect can be interpreted as the efficacy of deploying an app in real-world outpatient clinics, where overall uptake to clinical practice is likely less than 100%.

Aim 2

Sub-Aim 2.1: Formative Data Analysis. Core to the concept of formative evaluation is continual analysis of results and feedback to stakeholders. That will be done in this formative evaluation. Key data sources are qualitative interviews, surveys to assess ORC, and collection of detail about organizational characteristics and implementation process and progress. All qualitative interviews will be transcribed in full. Rapid analysis approaches will generate preliminary findings to share among the research team. This effort will involve an initial review of factors identified as directly impacting the process of supporting app implementation and impact of the apps on clinical workflow. Rapid analysis will be followed by in-depth content analysis. Content analysis to examine the telephone interviews will involve three phases: data coding, within-case analysis, and between-case analysis. In the data coding phase, we will use qualitative data analysis software (ATLAS.ti 5.0) to code the study data. The OTIE will provide a starting list of codes, which we will supplement with emergent codes as analysis proceeds. Using a common codebook, two investigators will conduct a preliminary test of codes by independently coding five transcripts. Based on the preliminary test, the investigators will sharpen the coding manual's definitions, decision rules, and examples. Research assistants will code the remaining documents.

In the second phase, we will conduct a within-case analysis of each VA using ATLAS.ti to generate reports of all text segments for each code. We will assess the degree to which the construct emerges in the data (its "strength"), the degree to which the construct positively or negatively affects implementation (its "valence"), and the degree to which relationships among constructs are consistent with the hypothesized model. We will assess support for the hypothesized relationships by using three criteria proposed by Trochim and Miles and Huberman. First, we will look for the overall covariance of the constructs (e.g., whether VA clinics exhibiting strong implementation climate have supportive administration). Second, we will look for explicit attributions or the identification of plausible mechanisms to link the two constructs (e.g., participants attribute a strong implementation climate to the deployment of appropriate implementation policies and practices).

In the third phase, we will apply the same criteria across the cases to determine if cross-case variation in implementation is consistent with the hypothesized relationships in the model. Consistent with the organization-level focus of the model, we will aggregate and analyze quantitative data on implementation policies and practices (e.g. staffing levels) and other study constructs using simple statistics. In addition, we will create within-case and between-case data displays that cross-tabulate the quantitative and qualitative data in order to facilitate the use of pattern-matching logic.

Sub-Aim 2.2: Collection of this data will be descriptively summarized to understand how rapidly sites meet key milestones as a result of the OCC implementation process, correlate the milestones to the number of patients serviced via the apps (i.e., reach), and allow for stratified analyses of main quantitative study results by degree of implementation based on reaching milestones to determine if the apps are more effective among sites that have reached more implementation milestones. We will analyze the qualitative data from the interviews in the same manner as described above for the formative evaluations using direct content analysis to examine themes within each case and to determine cross-case variation.

8.14 REFERENCES: List only the 5-10 most relevant references (a separate bibliography can be attached for reference purposes if this study involves novel approaches, agents, or an emerging technology that the IRB may not be familiar with):

1. Landow, S.M., D.H. Oh, and M.A. Weinstock, *Teledermatology within the Veterans Health Administration, 2002-2014*. *Telemed E Health*, 2015. **21**(10): p. 769-773.
2. Kilbourne, A.M., M.S. Neumann, H.A. Pincus, et al., *Implementing evidence-based interventions in health care: application of the replicating effective programs framework*. *Implement. Sci.*, 2007. **2**: p. 42.

3. Neumann, M.S. and E.D. Sogolow, *Replicating effective programs: HIV/AIDS prevention technology transfer*. AIDS Educ. Prev., 2000. **12**(5 Suppl.): p. 35-48.
4. Moullin, J.C., D. Sabater-Hernandez, F. Fernandez-Llimos, et al., *A systematic review of implementation frameworks of innovations in healthcare and resulting generic implementation*. Health Res. Policy Syst., 2015. **13**: p. 16.
5. Klein, K. and J. Sorra, *The challenge of innovation implementation*. Academy of. Management Review, 1996. **4**: p. 1055-1080.

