Aim 1. Measure impact of apps on access to dermatology care. *San Francisco VA Health Care System's involvement is limited in Aim 1. All data related to this aim is collected by the VA's Center for Access Policy, Evaluation Research (CAPER) located at the Boston VA Health Care System. All data collected from the Corporate Data Warehouse, or any other databases as approved by the Boston VA Health Care System IRB will be anonymously recorded, aggregated, and shared with investigators and study staff at the San Francisco VA Health Care System and other sites. No analysis of the primary data will occur at San Francisco VA.*

Both apps will be made available over a 2 year period in a randomized, stepped-wedge design to Veterans Health Administration (VHA) facilities, after each app becomes available. The *VA Telederm* app will be distributed to 36 eligible VHA facilities that currently have low teledermatology activity and thus have had relatively poor adoption of basic consultative teledermatology. The *My Telederm* app will be distributed to 24 facilities with dermatology clinics that currently have relatively high teledermatology activity and thus already have relatively mature teledermatology programs ready for advanced operations.

By using health factors and stop codes unique to each app, we will use the VA Corporate Data Warehouse (CDW) to measure the impact of both apps on the following outcomes reflecting dermatology access: 1) Consult and appointment completion times for both teledermatology and in-person consults, stratified by new and established patients (primary outcome); 2) Instances of

dermatologic care (associated with either teledermatology or in-person dermatology encounters); and 3) Travel costs for VA, as well as non-VA care consult rates and associated costs. In addition, the following outcomes will be measured specifically for the *My Telederm* app: 1) Proportions of new patient encounters in-person dermatology clinics; and 2) “No-show” rates and timeliness of follow-up. Results of each of these access measures will be stratified to examine the effect on rural/highly rural Veterans, as well as to determine whether a differential effect occurs for facilities with some pre-existing teledermatology relative to those that had none.

Aim 2. Determine the factors that affect personal and organizational adoption of mobile apps.

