In **Aim 1**, the number of participating medical center facilities (clusters) was determined as follows: The inclusion criterion for the first trial (*VA Telederm*) was that a site had a minimum of 0.1% and < 8.8% of its total FY 2016 dermatology encounters were attributable to teledermatology (stop codes 695/696). We also used clinical FTE data from FY 2016 and FY 2017 to make sure that they had at least some dermatologists on staff available. VA medical centers with no teledermatology activity in FY 2016 or with zero full-time equivalent dermatologists were excluded. In total, we identified 36 sites eligible for *VA Telederm*. Conversely, the inclusion criterion for the second trial with *My Telederm* was that a site had $\geq 8.8\%$ of all FY 2016 dermatology encounters as teledermatology. This indicated considerable pre-existing experience with consultative teledermatology and the likely presence of dermatology reader and support personnel needed to implement *My Telederm*. We determined, based on average treatment effects in the literature, that under most scenarios we are well-powered to detect conservative differences of 10% from baseline.

In **Aim 2**, as described in 10.1 above, we anticipate that 16-17 subjects will be enrolled for formative evaluation at each of the three sites (San Francisco, Denver and Providence). Each job title has been selected since it will either play be end-users of the mobile app program (e.g., primary care provider or imager or dermatologist), or be important support staff or mediators (e.g., Clinical Application Coordinator, program support assistants), or will be important leadership whose buy-in is necessary for successful implementation (clinical leadership). Sub aim 2.2 an additional 4 sites, two that have used the apps extensively in the last year and two that have not will provide additional insight into the facilitators and barriers at these sites.

10.4 * PARTICIPANT AGE RANGE: Eligible age ranges: (REQUIRED)

- 0-6 years
- 7-12 years
- 13-17 years
- 18-64 years
- 65+

10.5 * STUDY POPULATIONS: Data will be collected from or about the following types of people (check all that apply): (REQUIRED)

- Inpatients
- Outpatients
- Family members or caregivers
- Providers
- People who have a condition but who are not being seen as patients
- Healthy volunteers
- Students
- Staff of UCSF or affiliated institutions
- None of the above

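### Questions about whether an app works better in one group than another are to be answered from stratified results, with no app-by-subgroup contrast in the model and no exploratory label

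*Combined protocol and SAP*

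**What the plan says.** Three places bear on this.

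- **Section 8.2, Aim 1.** One sentence has two purposes, and both are to be met by stratifying every access measure. It begins "Results of each of these access measures will be stratified to examine the effect on rural/highly rural Veterans, as well as to determine whether a". Its first purpose is thus rurality. Its second is to look for a "differential effect occurs for facilities with some pre-existing teledermatology relative to those that had none".
- **Section 8.13, Sub-Aim 2.2.** Stratified analyses of the main results by milestones reached are planned "to determine if the apps are more effective among sites that have reached more implementation milestones".
- **Section 8.13, Aim 1 data analysis.** The model is described thus: "we will analyze the data using mixed models that allow for time fixed effects and cluster random effects". An instrumental-variable analysis and an intent-to-treat analysis follow. No app-by-subgroup term, rule for declaring that strata differ, multiplicity handling or exploratory label is given.

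Section 8.13 opens its Aim 1 text by reporting that poor site participation, partly in the pandemic, meant the plan could not be followed. The work turned instead to factors associated with completing consults through the apps, including rural and urban differences. No contrast is stated for that either.

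**The concern.** Whether an effect differs between two groups is a question about the difference of two effects. It needs an estimate of that difference and its standard error. Two separate stratum results supply neither. Readers given only those results tend to compare significance, and a smaller stratum can miss significance while a larger one reaches it although the true effect is the same in both.

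Rurality adds a complication. Rural and urban Veterans attend the same facilities in the same quarters, so their stratum estimates share variation. That variation cancels in a joint contrast. It does not cancel when two separate fits are treated as unrelated, so a real difference could also be missed.

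At stake is a false statement that an app helps one group of Veterans or sites and not another, carried forward without an exploratory label.

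**Working it through.** **The plan's own figure.** The only design statement for Aim 1 is in section 10.3 (repeated in 10.7): "under most scenarios we are well-powered to detect conservative differences of 10% from baseline". It cannot be reproduced, because alpha, numeric power, standard deviation, intracluster correlation, cluster size and baseline are not given. No subgroup error rate is stated.

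**Inputs for the illustration, all assumed.** Two-sided alpha 0.05; overall power 80%; the same true effect in both strata; stratum estimates independent; share of information f in the smaller stratum between 0.2 and 0.5; strata declared different when exactly one is significant.

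**Formulas.**

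- Overall non-centrality = 1.960 + 0.842 = 2.802.
- Stratum power = Φ(2.802 × √share − 1.960).
- P(exactly one significant) = p1(1 − p2) + p2(1 − p1).

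**Results at 80% overall power.**

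- f = 0.5: 2.802 × 0.707 = 1.981, so p1 = p2 = Φ(0.021) = 0.508. Discordance = 2 × 0.508 × 0.492 = 0.500.
- f = 0.2: p1 = Φ(1.253 − 1.960) = 0.240 and p2 = Φ(2.506 − 1.960) = 0.707. Discordance = 0.240 × 0.293 + 0.707 × 0.760 = 0.608.

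**Sensitivity.**

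| Change in assumption | P(exactly one significant) |
|---|---|
| Power 90%, f = 0.5 / 0.2 | 46.6% / 62.7% |
| Power 95%, f = 0.5 / 0.2 | 40.1% / 60.8% |
| Power 99%, f = 0.5 / 0.2 | 24.4% / 51.6% |
| Power 80%, correlation 0.5, f = 0.5 / 0.2 | 33.3% / 51.2% |
| Power 80%, correlation 0.7, f = 0.5 / 0.2 | 25.3% / 48.2% |
| Power 80%, shared facility-quarter variance 1% of consult variance, rural one-third / 20% | 41% / 51% |
| Same, shared variance 3% | 28% / 37% |

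The last two rows assume 100 consults per facility-quarter in a layout of 36 or 24 sites, 10 quarters and 8 steps. A correctly specified interaction test gives 5% per contrast in every case.

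**Is an interaction term enough for rurality?** Not on its own. I used the same layout with rural share 20% to 33% and facility variance 2% of consult variance, all assumed. I let each facility's rural and urban levels vary independently, and compared the model-based variance of the app-by-rurality estimate with its true variance.

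| Facility-by-rurality variance (share of consult variance) | False rejection, term omitted | False rejection, term included |
|---|---|---|
| 0 | 5% | 5% |
| 1% | 19% to 24% | 5% |
| 3% | 37% to 44% | 5% |

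**Power of the interaction test.** For an interaction as large as the overall effect, power = Φ(non-centrality × √(f(1 − f)) − 1.960). At 80% overall power, f = 0.2 gives Φ(1.121 − 1.960) = 20% and f = 0.5 gives Φ(1.401 − 1.960) = 29%. At 95% overall power the values are 30% and 44%.

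**Multiplicity.** Section 8.2 lists three outcome groups for both apps and two more for My Telederm, with two stratifiers. At 5% each, and assuming independence, the chance of at least one false difference is 1 − 0.95^6 = 26.5% for six contrasts and 1 − 0.95^10 = 40.1% for ten. Low power and this multiplicity both argue for an exploratory label.

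**The case against.** The strongest reply is that the plan is silent here and has not chosen a wrong method. Four parts of that reply deserve an answer.

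- **No decision rule is stated.** Correct. A reader might infer that strata will be declared different when one is significant and the other is not. No section says so. The percentages show what would follow from that common default; they do not describe the plan.
- **Rurality is not given a differential purpose.** Correct. Section 8.2 attaches the differential question to pre-existing teledermatology. For rurality it proposes only to examine the effect, and estimating an effect in a named stratum is legitimate. The interaction is needed if a rural-versus-urban statement is made. The factor that does carry the differential question has its own difficulty: sections 8.5, 10.3 and 10.8 exclude sites with no FY 2016 activity, so at facility level its comparison group looks empty. The illustration does not apply there, and those sections need reconciling with 8.2.
- **The Aim 1 plan was not followed.** This stands and limits the reach of the point. However, the replacement work described in 8.13 includes rural and urban differences, so the issue can return in reporting.
- **The section is a brief summary.** Section 4 places Aim 1 outside the focus of this application, and Aim 1 is analysed elsewhere under separate approval. A fuller plan may exist. Even so, 8.2 and Sub-Aim 2.2 name stratification as the means of judging a difference, which goes beyond leaving out a detail.

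**Conclusion.** The point holds in a limited form. Sections 8.2 and 8.13 (Sub-Aim 2.2) intend to judge differences in effect from stratified results, and the 8.13 model contains no contrast that could do so. Under the assumptions listed, comparing strata by significance would suggest a difference in about 50% to 61% of analyses when there is none. Power of 80% to 99% with the same splits and independent strata widens this to about 24% to 63%, and shared facility-quarter variation lowers it. None of these inputs is in the documents, so the figures show the order of the problem and are not the trial's error rate.

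The documents do not support saying that the trial has reported, or will report, a false rural-urban difference: rurality is not assigned a differential test, and the Aim 1 plan was set aside. The recommendation applies to any Aim 1 comparison still run or reported.

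**What to change.** In sections 8.2 and 8.13, state that any claim that an app effect differs between groups will come from one mixed model per access measure, fitted to all groups together, with app release, subgroup, app-by-subgroup and subgroup-by-quarter terms. For rurality, include facility, facility-by-rurality and facility-by-quarter random effects. Base the claim only on the interaction estimate and its confidence interval. Show stratum effects from the same model as description, and label the subgroup results exploratory. Use the same form for the milestone comparison in Sub-Aim 2.2.

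The cost is a few sentences and some extra model terms. Section 10.1 already plans to record rurality for individual encounters. The downside is low interaction power, roughly 20% to 44% in the illustration for an interaction as large as the overall effect, so fewer subgroup differences will be claimed.
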